6 STUDY DRUG

6.1 IDENTITY OF PLECANATIDE AND PLACEBO

Plecanatide is a synthetic hexadecapeptide that is an analog (identical, with the exception of a single amino acid) of uroguanylin, a natural hormone. The chemical name, molecular formula, molecular weight, and amino acid sequence of plecanatide can be found in the IB provided to each clinical site.

The drug product is a tablet comprised of plecanatide, microcrystalline cellulose, and magnesium stearate. Matching placebo composition is identical but does not contain plecanatide. Both plecanatide and placebo tablets are manufactured by UPM Pharmaceuticals (Bristol, TN) and packaged by Sharp Packaging Solutions (Allentown, PA). Study supplies will be retested as required by the sponsor.

6.2 ADMINISTRATION

Study drug will be administered for 8 consecutive weeks according to the randomization scheme displayed in **Table 3**. Each patient will take one tablet orally (by mouth) daily preferably at the same time each day—**in the morning**—with approximately 240 mL (~8 oz.) of liquid, with or without food.

No dose adjustments will be allowed on this study.

Table 3 Treatment Arms

Table 3: Treatment Arms

Treatment Arm	Treatment	Number of Patients
1	0.5 mg plecanatide	30
2	1.0 mg plecanatide	30
3	1.5 mg plecanatide	30
4	Matching placebo	30

Overdose

Plecanatide has minimal systemic absorption, therefore standard treatment measures for the symptomatology being exhibited should be provided. Notable, plecanatide was generally well-tolerated after single doses up to 48.6 mg and multiple doses up to 9.0 mg for 12 weeks in prior studies.

Individual Patient Stopping Criteria

Adverse events due to study drug that affect individual patient safety may necessitate dose interruptions or early discontinuation as described in this section.

Plecanatide therapy in adults with CIC has caused diarrhea in 5% of patients with severe diarrhea occurring in 0.6% of patients. Severe diarrhea may cause dehydration. Pediatric patients may be at increased risk for diarrhea and dehydration with plecanatide therapy.

In general, study drug dosing should not be modified for mild diarrhea (Grade 1: increase of <4 stools per day over baseline) or mild dehydration (Grade 1: dry mucous membranes, diminished skin turgor) (Guidance for Industry, FDA, 2007). If study drug is not well tolerated by an individual patient, treatment will be permanently discontinued for that patient.

The following guidelines should be used in the case of moderate or severe diarrhea or dehydration:

Table 4 Individual Patient Stopping Criteria

Worst Observed Toxicity Grade (Guidance for Industry, FDA, 2007)	Dose Modification for Study Drug
Diarrhea	
Grade 2: Increase of 4-6 stools per day over baseline	No intervention required
Grade 3: Increase of ≥ 7 stools per day over baseline, incontinence, hospitalization indicated	Interrupt study drug for <7 days until resolved to less than Grade 2 severity. If diarrhea was study drug-related, permanently discontinue study drug. If diarrhea was not study drug-related, eg, viral gastroenteritis, then consider resuming treatment after consultation with Sponsor's Medical Monitor
Grade 4: Life-threatening consequences, urgent intervention indicated	Permanently discontinue study drug
Dehydration	
Grade 2: IV fluids indicated <24 hour	Interrupt study drug for <7 days until resolved to less than Grade 2 severity. If dehydration was study drug-related, permanently discontinue study drug. If dehydration was not study drug-related, consider resuming treatment after consultation with Sponsor's Medical Monitor
Grade 3: IV fluids or hospitalization indicated	Permanently discontinue study drug
Grade 4: Life-threatening consequences, urgent intervention indicated	Permanently discontinue study drug

Study Stopping Criteria

Dosing of all patients in the study will be interrupted for at least one week if ≥ 2 patients receiving study drug develop drug-related Grade 3 diarrhea and/or dehydration or if one patient

develops drug-related Grade 4 diarrhea and/or dehydration. This will allow the Sponsor to assess whether the trial should be stopped or modified.

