5.2.6 Early Withdrawal Visit (EW)

Patients are free to withdraw from participation in the study at any time. Investigators may choose to discontinue a patient's participation in the study if they believe it is in the patient's best interest clinically. If a patient's post-randomization compliance is of concern, contact the medical monitor to discuss. If the patient has an intervening illness that requires discontinuation of study participation, the patient and Investigator will follow procedures for early withdrawal. The following are examples of AEs that qualify for Early Withdrawal (EW):

- A positive pregnancy test will require discontinuation from the study (see **Section 7.7**).
- Changes in laboratory values, PE findings, or other assessments considered by the Investigator (or designee) to be clinically significant will require discontinuation from the study.
- Clinically significant TEAEs, including clinically significant laboratory test abnormalities or SAEs regardless of relatedness to study treatment that cause the patient, investigator, or Sponsor to feel it is not in the patient's best interest to continue.

A patient may also be withdrawn from study drug/study by the Sponsor, regulatory authorities, or the institutional review board (IRB). Patients will also be withdrawn if the entire study is terminated prematurely as described in **Section 9.10**.

Patients who discontinue early from the study should, if possible, have an Early Withdrawal Visit. The Investigator must make every effort (with proper documentation) to have the patient complete this final visit. This visit should take place as soon as possible (and within 5 days) after the patient stops taking study drug.

The following procedures will be performed at the Early Withdrawal Visit:

- Collect/record unused study drug from the supply dispensed at the previous visit
- Review the electronic diary compliance reports and re-emphasize the need for diary compliance, as necessary
- Have the patient complete the PRO questionnaires (see Study Procedure Manual)
- Assess/record changes in concomitant medications and diet
- Physical examination (including body weight) and vital signs (seated blood pressure, heart rate, respiration, and body temperature)
- 12-lead ECG (semi-recumbent)
- Safety laboratory assessments (hematology, serum chemistry, urinalysis)
- Perform urine pregnancy test, if applicable
- Collect blood samples for plecanatide/SP-338 and immunogenicity assessments

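### In Table 4, dehydration Grade 2 lies wholly inside Grade 3, so the individual action for unrelated cases and the count toward the study-wide pause for drug-related cases are undefined

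*Combined protocol and SAP*

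**What the plan says.** Table 4 (Section 6.2) selects the action by "Worst Observed Toxicity Grade (Guidance for Industry, FDA, 2007"). Its two relevant dehydration rows are:

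- "Grade 2: IV fluids indicated <24 hour": interrupt study drug for less than 7 days until the event falls below Grade 2. Then, by cause: "If dehydration was study drug-related, permanently discontinue study drug"; or "If dehydration was not study drug-related, consider resuming treatment after consultation with" the Sponsor's Medical Monitor.
- "Grade 3: IV fluids or hospitalization indicated": permanently discontinue study drug, with no condition on cause.

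The Study Stopping Criteria, directly after the table, use the same numbered grades: "Dosing of all patients in the study will be interrupted for at least one week" if at least two "patients receiving study drug develop drug-related Grade 3 diarrhea and/or dehydration or if one patient" has a drug-related Grade 4 event.

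Section 5.2.6 gives examples of events that qualify for early withdrawal. Its second bullet says that changes in laboratory values, physical examination findings or other assessments "considered by the Investigator (or designee) to be clinically significant will require discontinuation from the study". Its third bullet covers clinically significant treatment-emergent events regardless of relatedness, where the patient, investigator or Sponsor judges that continuing is not in the patient's interest.

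**The concern.** A grading table works only if each patient falls in one row. Here the lower dehydration grade has a time limit and the higher one has none, so the higher definition takes in the whole of the lower one. Two things hang on the row chosen: what happens to the individual patient, and whether the event counts toward a pause in dosing for everyone.

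The pause rule is the only numerical study-level safety trigger in the protocol. No interim analysis is planned (Section 8.11), and termination under Section 9.10 is discretionary. Section 6.2 itself says that pediatric patients may be at greater risk of diarrhea and dehydration, and about 40 sites must apply the table. Section 7.3.2 cannot settle the grade, because it rates severity as mild, moderate or severe without numbers.

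There is also a smaller path into the efficacy data. Patients withdrawn after randomization are not replaced (Section 5.2.6), and weeks with no recorded bowel movement response after withdrawal are set to an SBM rate of 0 (Section 8.4.1). I have not sized that effect, and the documents give nothing to size it with.

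**Working it through.** The plan states no figure on this point, so there is none to reproduce. The check is mainly a reading of the rules side by side.

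**Step 1: overlap.** Grade 2 requires that IV fluids are indicated and that the duration is under 24 hours. Grade 3 requires that IV fluids are indicated, for any duration, or that hospitalization is indicated. Anyone who meets the first definition meets the IV-fluids limb of the second, so Grade 2 is a subset of Grade 3. The diarrhea rows of the same table do not have this problem in their stool counts: 4 to 6 per day over baseline against 7 or more.

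**Step 2: tie-breaker.** If the worst-grade header decides, every patient in the Grade 2 row moves to Grade 3 and the Grade 2 row is empty. If it does not decide, both rows apply. Either the rows conflict or one of them has no effect.

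**Step 3: consequence by cause**, for a patient with IV fluids indicated for under 24 hours and no hospitalization:

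| Cause | Action if Grade 2 | Action if Grade 3 | Do end actions differ? | Counts toward pause if Grade 2 / Grade 3 |
|---|---|---|---|---|
| Not drug-related | Interrupt, consider resuming after consultation | Permanently discontinue | Yes | No / No |
| Drug-related | Permanently discontinue | Permanently discontinue | No | No / Yes |

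The two ambiguities fall on different patients. The table's own diarrhea example shows that the first row is foreseeable. Grade 3 diarrhea from viral gastroenteritis may lead to resumption. If that patient also has IV fluids indicated for under 24 hours, the dehydration rows give both answers.

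**Step 4: how far the grade could move the pause.** Let p be the per-patient rate of drug-related dehydration with IV fluids indicated for under 24 hours. The documents do not give p, so it is an assumption shown over a range. Assume also that patients are independent and that there are no other qualifying events. If these events are graded 3,

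P(pause) = 1 − (1 − p)^n − n·p·(1 − p)^(n−1).

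Example with n = 90 (three active arms of about 30) and p = 1%: 1 − 0.99^90 − 90 × 0.01 × 0.99^89 = 1 − 0.4047 − 0.3679 = 0.227.

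| Assumed p | n = 90 | n = 120 |
|---|---|---|
| 0.2% | 0.014 | 0.024 |
| 0.5% | 0.075 | 0.122 |
| 0.6% | 0.102 | 0.162 |
| 1% | 0.227 | 0.338 |
| 2% | 0.540 | 0.695 |
| 3% | 0.756 | 0.878 |

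The column for 120 covers the case where relatedness, judged blind, is also assigned to placebo patients. The 0.6% line matches the adult rate of severe diarrhea in Section 6.2, which is not a dehydration rate and serves only as a point of reference. If the same events are graded 2, they contribute nothing to the pause and each probability is zero.

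**Step 5: Section 5.2.6.** Its second bullet requires leaving the study once a change is judged clinically significant, and it has no condition on cause. The Grade 2 row allows resumption of drug when the cause is unrelated. A patient whose findings are judged clinically significant and whose dehydration is unrelated is covered by both.

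**The case against.** A reader might infer that the two rows give opposite actions, that Section 5.2.6 adds a third, and that one patient could be resumed, stopped or withdrawn while the pause also hangs in the balance. The documents do not support that reading, for these reasons.

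- The Grade 2 row also ends in permanent discontinuation when the dehydration is drug-related. End actions differ only for unrelated cases, and there resumption is only to be considered, after consultation with the Medical Monitor. That consultation is a central check on the one branch where individual actions diverge.
- Resumption needs an unrelated event and the pause counts only drug-related ones, so no single patient faces both ambiguities. One Grade 3 patient does not trigger the pause; two are needed.
- Section 5.2.6 is a general list of examples that depends on a judgement of clinical significance and does not name dehydration. Its third bullet, on treatment-emergent events, leaves the decision to judgement. It also times the Early Withdrawal Visit from the stopping of study drug, so stopping drug and leaving the study are not shown to be separate paths.

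It can also be said that Table 4 is introduced as guidelines, and that the worst-grade header points toward stopping drug and counting the event, so unsafe handling of an individual patient is not shown.

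All of this stands and limits the point. It does not remove the overlap. The Medical Monitor's consultation is written into the Grade 2 row only, so it does not decide which row applies. Using the header as the tie-breaker leaves a written instruction that can never be followed.

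**Conclusion.** The point holds in limited form. As worded, every Grade 2 dehydration patient also meets Grade 3. The individual action is contradictory for dehydration not related to study drug, and the count toward the study-wide pause is undefined for drug-related dehydration. Section 5.2.6 is a secondary tension with the resume option.

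The overlap and the two consequences rest on the text alone. Their practical size is not known. The probabilities of a pause (0.014 to 0.756 for 90 patients, 0.024 to 0.878 for 120) depend entirely on an assumed event rate of 0.2% to 3%. They show that the choice of row can matter to the pause rule, not that a pause is likely. The matter deserves correction because it bears on a safety rule for minors and costs little to put right.

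**What to change.** The sponsor should:

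1. Reconcile the Grade 2 and Grade 3 dehydration rows of Table 4 so that no patient can meet both.
2. State in the Study Stopping Criteria that the pause rule uses the reconciled grades.
3. State whether Table 4 or Section 5.2.6 governs for diarrhea and dehydration.

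The choice of criteria and actions is the sponsor's, and none is proposed here. The cost is a wording amendment to Table 4 and the Study Stopping Criteria and a cross-reference in Section 5.2.6. It needs no new data, visits or patients.

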6.3 PACKAGING, LABELING AND STORAGE

All study centers will be provided with adequate supplies of study medication—plecanatide tablets at 3 dose strengths (see **Table 3**) and identically appearing placebo tablets, by Sharp Corporation.

6.3.1 Packaging

Each investigational drug kit will contain a 4-week supply in blister packaging—a total of 32 tablets, including 4 extra tablets to allow for a 3-day window extension for a study visit. Individually blister packaged tablets will be provided in four connected strips (each per 1 week) as a 4-panel key-pack that folds into a carton. The two bottom panels fold up into the two top panels, nesting blister cavities. Instructions for releasing a tablet from the blister dome are printed on the outside of the carton.

At each dispensing visit, each patient will be given a numbered drug kit corresponding to the treatment group into which the patient was randomized. At the randomization visit (Day 1 of the Treatment Period), the eligible patient will receive one drug kit for the first 4 weeks of dosing (weeks 1, 2, 3 and 4). At the Week 4 Visit, the patient will receive a new drug kit for their weeks 5, 6, 7 and 8 of dosing. Patients are instructed to bring their kits at the following study visit to allow for determination of compliance and reconciliation of supplies.

Save all empty packaging or packaging containing unused tablets for final disposition by the sponsor or contract pharmacy.

6.3.2 Label

Each of the investigational drug kits will have a unique label containing the following information: protocol number, drug kit number, contents, directions for use, storage conditions, Sponsor name, address and the statements: “Caution: New Drug - Limited by Federal Law to Investigational use. Investigational Drug – To be used by Qualified Investigator Only. For Clinical Trial Use Only. Keep Out of Reach of Children under the age of 12”.

The label will include the following fields to be completed by site personnel: Investigator name and phone number, patient number and treatment weeks. When dispensing a kit to a patient, complete and remove the tear off portion of the label and keep this in the source documents. At each monitoring visit, the source document records will be verified against the IWRS assignment.

There will also be a smaller label on the carton spine that identifies the study number and drug kit number and Sponsor.

6.3.3 Storage

The Investigator, or qualified designee, is responsible for the proper storage of the study medications according to the Sponsor's recommendations and all applicable federal/state regulatory guidelines. At the clinical site, plecanatide should be stored at controlled room temperature 20 to 25°C (68 to 77°F) in a secure area with Min / Max Temperature Recording

with restricted access. Deviations from Sponsors recommendations / guidelines should be reported, as directed in the Site Level Temperature Excursion Reporting Form.

Patients will be instructed to store their study drug at room temperature defined for this study as 20 to 25°C (68 to 77°F).

The Investigator must agree not to dispense or store the investigational drug at any location other than that listed on the Form FDA 1572.

6.4 BLINDING AND BREAKING THE BLIND

The study will be performed in a double-blind manner. All study drugs will be supplied in identical blister packs and tablets will be similar in color, smell, taste, and appearance, thereby assuring double-blind conditions.

In the event of a need to break the blind, the Investigator at the clinical site will have the ability to break the treatment code using the IWRS. The blind should only be broken following discussion on a case-by-case basis, with the Sponsor/Medical Monitor (except in a medical emergency). The Sponsor's Medical Monitor will also be granted emergency code-break privileges using the IWRS. All telephone calls resulting in an un-blinding event will be documented. The Sponsor and CRO, as applicable, will specify who in each company is able to review unblinded treatment in a blinded trial.

In the event of a treatment code-break, the time, date, reason, name, and signature of the person responsible for breaking the code must be fully documented in the patient's source documents and any associated AE recorded. The breaking of the blind will result in the withdrawal of the patient from study participation, and the patient should follow the procedures detailed for Early Withdrawal Visit study assessment (see **Section 5.2.6**).

The overall randomization code for the study will be broken at study completion. This will occur once all final clinical data have been entered into the database, data queries have been resolved, and the assignment of patients to the analysis sets has been completed.

6.5 DRUG ACCOUNTABILITY

Acknowledgement of receipt of drug shipments and distribution of all investigational drug kits will be recorded using the IWRS. The drug inventory log can be generated from IWRS at the site level as a standard report.

In addition, accurate records of study drug dispensed to patients will be kept by the Investigator, or qualified designee, specifying the kit number, the patient number assigned, and the amount dispensed to each patient and the date dispensed. This information will be available in the IWRS and the drug accountability log for the overall study. At each visit after Visit X, the patient is asked to return their previously dispensed drug kit and the number of remaining tablets is entered into the eCRF for drug accountability.

A blinded drug accountability log can also be generated from IWRS and must be available for inspection at each monitoring visit and at the completion of the study. At the completion of the study, the Investigator will provide copies of this accountability log to the Sponsor.

The Investigator is responsible for assuring the retrieval of all study supplies from patients. At the completion of the study, all unused investigational drug kits will be returned to a third party in accordance with the Sponsor's (or designee's) written instructions. The Investigator must verify that all unused or partially used study drug supplies have been returned by the patient and that no remaining supplies are in the Investigator's possession.

6.6 COMPLIANCE

Patients will be advised as to how to take their daily medication and will return all unused study drug to the clinical site at each visit during the Treatment Period. The number of remaining tablets will be counted and entered into the appropriate eCRF page for that patient. Patients unwilling or unable to maintain compliance with study drug administration or procedures may be discontinued from the study at the discretion of the investigator in conjunction with the medical monitor.

7 ASSESSMENT, REPORTING, RECORDING AND FOLLOW UP OF ADVERSE EVENTS

7.1 DEFINITION

An AE is any untoward medical occurrence associated with the use of a drug in humans, whether or not considered to be drug related. An AE can therefore be any unfavorable and unintended sign (including abnormal laboratory finding), symptom, or disease temporally associated with the use of an investigational product or study procedure whether or not considered related to the product or procedure.

NOTE: Specific gastrointestinal symptoms related to CIC are recorded daily in the electronic Diary in response to standardized questions, and are BOTH efficacy AND safety response variables. These symptoms are abdominal bloating, abdominal pain, abdominal discomfort, straining with bowel movement and pain with defecation. The diary is a “real-time” patient reported outcome record that is based on “within 24 hours” patient recall. Because these symptoms are considered adequately recorded in the CIC Symptom Diary, they should generally not also be reported in the adverse event database that relies on a much longer patient recall period. In order to prevent double-recording of a single specific event, the daily CIC Symptom Diary record is considered the highest quality record of an event and should therefore be the only record of the same event.

All AEs, including intercurrent illnesses and regardless of the source of identification (e.g., physical examination, laboratory assessment, electrocardiogram (ECG), reported by patient), occurring during the study will be documented in the eCRF. Concomitant illnesses that existed before entry into the study will not be considered AEs unless they worsen during the treatment period.

Adverse events occurring from the time of signing the informed consent form (ICF) up to the intake of the first dose of study medication will be classified as pre-existing conditions for the study and therefore will be recorded in the Medical History page of the electronic case report form (eCRF). Serious adverse events (as defined below) occurring after the signing of informed consent but before randomization (i.e., during screening) will be collected and reported as such. A treatment emergent adverse event (TEAE) is defined as an AE that begins or worsens in frequency and/or severity after at least one dose of study drug has been administered.

Minor fluctuations in laboratory values for standard monitoring (abnormal values) that the investigator does not consider clinically significant or related to study drug will not be recorded as AEs. However, if the laboratory abnormality is associated with a diagnosis, then the AE term for that diagnosis will be reported.

